8.4. Assessment of exploratory biomarkers

- Serum and plasma samples collected will also be stored (at baseline and at Week 24 for (but not limited to) future evaluation of disease categorisation, auto-antibodies, inflammatory, immunological and vascular biomarkers and products of synovial, cartilage and bone turnover in this and future studies (subject to ethical review of such studies).

9. STUDY PROCEDURES BY VISIT

Note: All timed visits post-screening should take place within a seven-day window of the scheduled visit time.

All study visits falling outside this window will be reported to the Sponsor QA Office on the designated protocol deviation form, in-line with the corresponding Sponsor SOP.

9.1 Summary schedule of study assessments

Timepoint	Wk -4 to 0	Wk 0	Wk 4*	Wk 12*	Wk 24*	Unscheduled Visit
Study phase	Screening	Baseline	Safety	Secondary outcomes	Primary outcome	-
Visit	1	2	3	4	5	6
Inclusion/Exclusion Criteria	x	x				
Informed Consent ¹	x	x	x	x	x	x
Randomisation		x				
Adverse event assessment			x	x	x	x
Patient demographic data	x					
Vital signs/observations (height, weight, BP, heart rate, temperature)	x					
Medical/surgical/family history	x					
Concomitant medications	x	x	x	x	x	x
Clinical assessment data (TJC & SJC [via IJA], DAS28, EMS)	x	x	x	x	x	x ^a
General Physical Examination ²	x					
Patient reported outcome questionnaires (VAS pain, disease activity & general health, HAQ-DI)	x	x	x	x	x	x ^a
Autoantibodies (RF, ACPA, ANA) ³	x					
Naïve CD4 ⁺ T-cells ³	x			x	x	x ^a
Inflammatory markers (ESR & CRP)	x	x	x	x	x	x ^a
Stored blood sample for exploratory biomarkers		x			x	
Haematology (FBC)	x	x	x	x	x	x ^a
Biochemistry (eGFR, LFT, U&E)	x	x	x	x	x	x ^a

Timepoint	Wk -4 to 0	Wk 0	Wk 4*	Wk 12*	Wk 24*	Unscheduled Visit
Study phase	Screening	Baseline	Safety	Secondary outcomes	Primary outcome	-
Visit	1	2	3	4	5	6
MSK Ultrasound 26 joints and 6 tendons+		X			X	X ^a
Physician assessment of general health (VAS)	X	X	X	X	X	X ^a
Chest X-Ray ⁴	X					
TB (QuantiFERON) ⁵	X					
Hepatitis B (HB Antigen, HB core antibody) ⁵	X					
Hepatitis C ⁵	X					
HIV Screen ⁵	X					
Urinalysis [Dipstick] ⁶	X					
Pregnancy test ⁶	X					
IMP initial administration time point⁺		X				
Document steroid use, method of administration and dose		X	X	X	X	X
Adverse event recording			X	X	X	X
Compliance assessment (IMP)			X	X	X	X

1. Written consent at screening & checking of consent at subsequent visits
2. Full systems examination to include cardiovascular, respiratory and abdominal examination. This is mandatory at screening visit and may be performed if clinically indicated (system-dependent) at other visits.
3. If not done within 4 weeks (may have been routinely assessed in EAC)
4. If subjects have a chest x-ray performed within the last 24 weeks, a new chest x-ray will not be performed in order to minimize exposure to x-ray radiation.
5. If not already performed within the last 12 weeks (may have been routinely assessed in EAC)
6. Urinalysis and Pregnancy test can be repeated at other visits if clinically indicated.
 - a. These assessments will only be carried out if the reason for the “unscheduled visit” is a flare.

* The permitted window for these study visits is +/- 7 days.

+ Research activity to occur +/- 7 days from clinic visits.

9.2 Screening visit (Weeks -4 to 0)

The screening period should not last longer than four weeks. The aim of the screening visit is to identify a patient who might be suitable for inclusion in the study. The following will be performed at this visit (and recorded in the CRF):

- ***General***

- Obtain written consent: The patient will have received information, including the Patient Information leaflet, at least 24 hours before the screening visit. Their knowledge of the nature and objectives of the study will be verified and his/her informed consent will be obtained.
- Subject number assigned
- Check patient eligibility
- Patient demographic data:
 - Age (years)
 - Sex
 - Ethnic group
- Clinical observations:
 - Height (cm)
 - Weight (kg)
 - BMI calculation (kg/m²)
 - Blood pressure (mmHg) & heart rate (bpm)
 - Temperature
- Concomitant medications/allergy history
- Detailed surgical/medical/social history
- Detailed family history (autoimmune, vascular & rheumatic disease)
- Smoking history
- Alcohol intake (units/week)

- ***Laboratory Tests***

- Routine haematology and biochemistry suitable for diagnostic investigation: FBC, U&E, LFT & eGFR ml/min/1.73 m²
- ESR (mm/h) & CRP (mg/L)
- Rheumatoid factor (RF) titre+
- Anti-nuclear antibody (ANA) titre+
- Anti-citrullinated protein antibody (ACPA) titre+

- Naïve CD4⁺ T-cell measurement+
- Hepatitis B&C screen (Hep B surface antigen, Hep B core antibody, anti-HCV antibody)^{[11]*}
- HIV Screen*
- QuantiFERON test for TB*
- Urinalysis for blood, protein and nitrites to exclude infection/renal disease
- Pregnancy test for women with childbearing potential

**If not already performed within the last 12 weeks (may have been routinely assessed in EAC)*

+ If not already performed within last 4 weeks (may have been routinely assessed in EAC)

- ***Clinical assessment data***

- Joint examination performed by an independent assessor:
 - Tender joint count (28)
 - Swollen joint count (28)
- Disease activity score (DAS28)
- Clinical disease activity Index (CDAI)
- Simplified disease activity index (SDAI)
- Early morning stiffness (mins)
- Full physical examination (including cardio-respiratory and abdominal systems)

- ***Patient reported outcomes***

- Visual analogue scores of pain/disease activity/general health
- Physician assessment of general health
- HAQ-DI

Note: Whenever possible, physician VAS assessments should be performed by the same investigator

- ***Imaging***

- Chest X-Ray (if not been done within the last 24 weeks)

- ***Randomisation***

- Randomisation to treatment arms (for patients with abnormal T-cell status) can only happen once the investigation in possession of the T-cell report.

N.B. this must take place prior to the patient attending the baseline visit

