6.5.3. Randomisation process

- Patients with abnormal baseline naïve CD4⁺ T-cells will be randomised 1:1 and receive MTX with T2T care vs. Benepali® + MTX.
- The pharmacy at Chapel Allerton Hospital will prepare a randomisation schedule. A central randomisation method using randomly permuted block sizes will be used. The Trials team at Leeds General Infirmary will hold the master randomisation list and, as patients enter the study, they will be assigned the next available Patient ID Number and assigned to receive treatment with either MTX + Benepali® or MTX with T2T care.
- Informed written consent for entry into the trial must be obtained prior to randomisation, subject to the patient meeting the eligibility criteria. Randomization should take place as soon as possible after consent is obtained and T-cell status is known and must be performed by an authorized member of the clinical team at the site using the LTHT Pharmacy telephone randomisation service.
- The following information is required in order for the patient to be randomized. The person making the randomization telephone call should have all details to hand:
 - Patient initials and date of birth
 - Name of person undertaking randomisation [REDACTED]
 - Name of the treating investigator [REDACTED]
 - Confirmation of eligibility
 - Confirmation of written informed consent and date [REDACTED]
 - T-cell status
 - Confirmation that screening clinical data has been collected
- A unique trial patient identifier will be assigned at randomization. After randomization the research site will: [REDACTED]
 - Ensure that patients are notified of their appointment dates. [REDACTED] Notify the patients' GP of their participation in the trial via formal letter.
 - Following patient randomisation, the authorised person performing the randomisation must complete the Patient Randomisation form. The Patient Randomisation form will contain the patient's details (initials, date of birth, trial number) and the date of randomisation. LTHT Pharmacy will also complete a Patient Randomisation form. The Patient Randomisation form

completed by PTHT Pharmacy will contain the patient's details (initials, date of birth, trial number), the date of randomisation and treatment allocation. [1]
[SEP]

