6.5.4. Study blinding

- Patients will not be blinded to treatment. Patients will not be told their T-cell result however, those randomised to receive Benepali® will know they will have abnormal T-cell subsets as this will be outlined in the PIS.
- Clinicians will not be blinded to treatment or T-cell result, however the joint count will be conducted independently by a suitably qualified and competent individual (as an independent joint assessor [IJA]) to minimise bias. This individual will not be involved in patient care and will be instructed not to discuss disease activity or treatment with patients or Principal Investigator.
- Ultrasound scans will be performed by sonographers blind to treatment allocation and T-cell result; patients will be instructed not to discuss details of their treatment during their scan.
- Randomisation codes will remain blinded to clinicians recruiting to the study as these will be administered centrally.

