9.3 Baseline visit & IMP commencement (Week 0)*

* Visit to occur within 4 weeks after screening visit

- ***General***

- Confirm eligibility by review of inclusion/exclusion criteria and consent
- Clinical observations will be performed as per standard care (not required as a research parameter)
- Medication, allergy and co-morbidity check

- ***Clinical assessment data***

- Joint examination performed by an independent assessor:
 - Tender joint count (28)
 - Swollen joint count (28)
- Disease activity score (DAS28)
- Clinical disease activity index (CDAI)
- Simplified disease activity index (SDAI)
- Early morning stiffness (mins)
- Cardio-respiratory & abdominal examinations if clinically indicated

- ***Patient reported outcomes***

- Visual analogue scores of pain/disease activity/general health
- Physician assessment of general health
- HAQ-DI

- ***Laboratory tests***

- Routine haematology and biochemistry suitable for diagnostic investigation: FBC, U&E, LFT & eGFR ml/min/1.73 m²

- o ESR (mm/h) & CRP (mg/L)
- o Biologic blood sample collection for storage (exploratory biomarkers)
- o Urinalysis/pregnancy test if clinically indicated

- ***Imaging***

- o Power Doppler Ultrasound (PDUS) of standard set of 26 joints and 6 tendons for grey-scale (GS), power Doppler (PD), erosions (E) and osteophytes (O) and tenosynovitis (TSV) (+/- 7 days from clinic visit)
 - To be performed prior to first administration of study treatments

- ***Adverse event recording***

- ***Initiation of DMARD treatment as per T2T*** (up to 7 days from clinic visit).

- ***Initiation of Benepali® for ARM C*** (up to 7 days from clinic visit).

- o Patients taught how to self-inject

- ***Offer IM/IA/PO corticosteroids as appropriate (in line with standard practice)***

- ***Document steroid used, dose and method of administration***

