12.3. General statistical considerations

Unless otherwise specified, the last valid measurement before study medication administration will be utilized as the baseline value. In general, summary statistics [n (number of available measurements), arithmetic mean, standard deviation, median, minimum, and maximum] for quantitative variables and absolute and relative frequency tables for qualitative data will be presented.

Wherever possible the trial will be reported in accordance with the recommendations of the CONSORT (Consolidated Standards of Reporting Trials) statement.

This trial includes both a confirmatory comparison (arm A vs arm B) and a pilot comparison (arm B vs arm C). For comparisons between arms A and B, two-tailed significance tests will be conducted at the 5% level of significance. Comparisons between arms B and C will be purely descriptive.

A detailed statistical analysis plan (SAP) will be completed prior to the final lock of the database; any differences between the final analysis and the SAP will be documented in the trial report.

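### Protocol 9.2 and 6.5.3 randomise before the baseline visit but 9.1 schedules it at Week 0, so in Arm B vs Arm C the baseline DAS28 and the last eligibility check can follow a known open-label allocation

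*Protocol*

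**What the plan says.** **When randomisation happens.** Only patients with abnormal naïve CD4+ T-cells are randomised (Arm B or C); Arm A is assigned by T-cell result.

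- Protocol 9.2 (Screening visit, Randomisation item): "N.B. this must take place prior to the patient attending the baseline visit".
- Protocol 6.5.3: "Randomization should take place as soon as possible after consent is obtained and T-cell status is known". The items needed for the telephone call include confirmed eligibility and "Confirmation that screening clinical data has been collected"; no baseline-visit data are required.
- Protocol 9.1, schedule: the row "Randomisation x" has its mark under Wk 0 (Baseline), and the screening column is empty.
- Protocol 9.3, on the baseline visit: "Visit to occur within 4 weeks after screening visit".

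**Who knows the arm.** Protocol 6.5.4: "Patients will not be blinded to treatment". Clinicians are blinded neither to treatment nor to T-cell result. Patients are not told their T-cell result. The joint assessor is independent of care and instructed not to discuss treatment, but is not stated to be blinded.

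**What is done at Week 0.** Protocol 9.3 lists joint counts, DAS28, early morning stiffness, patient VAS scales, physician VAS and HAQ-DI, and also this step: "Confirm eligibility by review of inclusion/exclusion criteria and consent".

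**What counts as baseline.** Protocol 12.3: "the last valid measurement before study medication administration will be utilized as the baseline value". SAP 11.4 repeats this. SAP 11.2.2 (Table 3) takes assessments before the first IMP dose and uses the one closest to the scheduled day.

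**The concern.** In an open-label trial, a baseline measured after allocation is no longer guaranteed to be independent of the arm. A patient who knows whether etanercept is coming may rate general health, pain or stiffness differently. A clinician who knows the arm may weigh a discretionary exclusion differently, such as comorbidity judged significant by the physician (Protocol 6.3.2). A covariate affected in this way can bias an adjusted estimate, and a re-check made with the arm known can lead to selective loss.

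What is at stake is B vs C, the only randomised comparison. It carries no tests, but Protocol 12.5.2 uses it to judge proof of concept and to trigger sample size calculations for later work. Leaving out significance tests does not protect an estimate from bias.

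**Working it through.** **1. Timing.** Two text sections (9.2 and 6.5.3) place randomisation before the baseline visit, and one table entry (9.1) places it at Week 0. The table has no column between screening and baseline, so the mark may be a simplification. As written, though, the sections cannot all be followed.

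**2. Longest gap.** The T-cell test may already have been done in the 4 weeks before screening (9.1, note 3), so the report can be in hand at screening. Randomisation could then fall on the screening day, with baseline up to 4 weeks later: 4 × 7 = 28 days. A later report shortens the gap. No section says when the patient is told the arm.

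**3. Which value becomes the analysis baseline.** Screening values precede randomisation. Week 0 values are later, still before dosing and closer to study day 1, so under Protocol 12.3 and SAP 11.2.2 and 11.4 they normally replace the screening values.

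**4. Where baseline enters B vs C under the current SAP.**

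- 11.6.2: remission at Weeks 12 and 24, with the model of 11.5.1, which adjusts for baseline DAS28.
- 11.6.8: sustained remission, same model.
- 12.4: change from baseline in DAS28 at Weeks 12 and 24, with baseline also a covariate.
- Patient-reported and imaging outcomes are now descriptive only (11.6.3 to 11.6.6; 13.1).

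**5. Which exposed items feed DAS28.** SAP 7.1 gives DAS28 = 0.56√TJC28 + 0.28√SJC28 + 0.014·GH + 0.70·ln(ESR). General health VAS (GH) is wholly patient-rated. The tender count depends partly on patient response. ESR is a laboratory value. HAQ-DI, stiffness and physician VAS do not enter DAS28.

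**6. Size for one patient.** The documents give no reporting shift, so these are assumptions:

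| Assumed GH shift | Change in baseline DAS28 |
|---|---|
| 5 mm | 0.014 × 5 = 0.07 |
| 10 mm | 0.014 × 10 = 0.14 |
| 20 mm | 0.014 × 20 = 0.28 |
| 30 mm | 0.014 × 30 = 0.42 |

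**7. From covariate to estimate.** Suppose the mean baseline DAS28 in Arm C is displaced by δ relative to Arm B through reporting alone, and later scores are unaffected. In a linear model adjusted for baseline, with slope β of the follow-up score on baseline, the arm effect moves by −βδ; an unadjusted mean change moves by −δ. The documents give neither δ nor β, and the sign of δ is open, so the bias cannot be computed from them. The observed follow-up score, and hence remission status at DAS28 ≤ 2.6, does not depend on the baseline value.

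**8. Analysis set.** Protocol 12.4 puts all randomised patients in the full analysis set. SAP 11.2 (v3.0; change listed in 13.1) excludes those withdrawn before or during the baseline visit. With randomisation before baseline, a patient can be allocated, the arm can become known, and the patient can leave both the trial and the analysis set.

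**9. Sample size.** The stated 53 patients for A vs B reproduces: the pooled two-proportion formula (25% vs 68%, ratio 2.75:1, two-sided 5%, 80% power) gives 13.32 in Arm B and 49.94 in total; 49.94 × 1.05 = 52.43, rounded up to 53. The timing of randomisation does not enter it.

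**The case against.** Several safeguards stand. Eligibility is confirmed before the randomisation call, so Week 0 is a second check, not the only one. ESR cannot respond to expectation, and joint counts are done by someone outside patient care. Unadjusted odds ratios are reported beside the adjusted ones, and B vs C is descriptive.

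Stronger readings are tempting, but the documents do not support them:

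- *Patients are told their arm four weeks before baseline.* The protocol fixes when randomisation occurs, not when it is disclosed, and 4 weeks is a ceiling. In 6.5.3 the allocation is listed only on the pharmacy's form. That does not establish concealment, but the time of disclosure is simply not given.
- *The whole baseline is recorded with the arm known.* This is too broad for DAS28, given ESR and the independent assessor.
- *The primary comparison is compromised.* Arms A and B both start methotrexate, and patients are not told their T-cell result (6.5.4, 8.2), so patient-side exposure is small. Clinicians know the T-cell result whatever the randomisation date, and the physician VAS is not part of DAS28.
- *Patient-reported outcome estimates are biased by adjustment.* That applied to the plan in Protocol 12.5.2. The SAP has withdrawn those models.
- *The baseline shift is 0.3 to 0.6 DAS28 units.* This needs a 20 mm VAS shift (0.28) together with 9 instead of 6 tender joints (0.56 × (3 − 2.449) = 0.31). Neither has a source in the documents, and the sum describes one patient's covariate, not bias in an estimate.

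**Conclusion.** The contradiction between 9.2 with 6.5.3 and 9.1 is real. Under 9.2, the Week 0 patient-rated scores, physician VAS and eligibility re-check can follow a known allocation, because baseline is tied to dosing and treatment is open-label. The effect reaches the adjusted B vs C remission odds ratios and the B vs C change-from-baseline DAS28 analysis; A vs B is largely untouched on the patient side. The illustrative 0.07 to 0.42 rests wholly on assumed VAS shifts of 5 to 30 mm, and the resulting bias in the estimates, including its direction, cannot be derived from the documents. The reduced full analysis set in SAP v3.0 makes the point more serious, since it allows exclusions after allocation in the only randomised comparison. This should be corrected, as a limited but avoidable risk to the pilot comparison.

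**What to change.** **Protocol.** Reconcile 6.5.3, 9.1 and 9.2 so that the randomisation call follows the Week 0 eligibility check, joint counts, VAS scales, HAQ-DI and stiffness. Deleting the note in 9.2 alone is not enough, because 6.5.3 would still call for randomisation as soon as the T-cell result is known. State when and by whom the allocation is disclosed. If the order is kept, define baseline for B vs C as the last value before randomisation.

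**SAP.** For patients already randomised before baseline, add two B vs C sensitivity analyses:

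1. the models of 11.6.2, 11.6.8 and 12.4 with the pre-randomisation screening DAS28 as covariate and, in 12.4, as the change reference;
2. the remission analyses in all randomised patients, including those withdrawn before or during the baseline visit, with missing outcomes handled by the non-responder rule in 11.2.3.

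Report how many randomised patients withdrew or were found ineligible between randomisation and the end of Week 0, by arm.

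**Cost.** Screening DAS28 is already collected (Protocol 9.2), so the analyses need no new data. A screening value can be up to 4 weeks old and may be a slightly weaker covariate. With the later call, the arm is known only at the end of the Week 0 visit, so supply and the self-injection teaching listed for that visit must be fitted in then or within the existing 7-day start allowance in 9.3. Planned recruitment (54 months from February 2020, to about August 2024) may already be over. The protocol wording may then come too late, but the sensitivity analyses remain feasible.

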9.3 Baseline visit & IMP commencement (Week 0)*

* Visit to occur within 4 weeks after screening visit

- ***General***

- Confirm eligibility by review of inclusion/exclusion criteria and consent
- Clinical observations will be performed as per standard care (not required as a research parameter)
- Medication, allergy and co-morbidity check

- ***Clinical assessment data***

- Joint examination performed by an independent assessor:
 - Tender joint count (28)
 - Swollen joint count (28)
- Disease activity score (DAS28)
- Clinical disease activity index (CDAI)
- Simplified disease activity index (SDAI)
- Early morning stiffness (mins)
- Cardio-respiratory & abdominal examinations if clinically indicated

- ***Patient reported outcomes***

- Visual analogue scores of pain/disease activity/general health
- Physician assessment of general health
- HAQ-DI

- ***Laboratory tests***

- Routine haematology and biochemistry suitable for diagnostic investigation: FBC, U&E, LFT & eGFR ml/min/1.73 m²

- o ESR (mm/h) & CRP (mg/L)
- o Biologic blood sample collection for storage (exploratory biomarkers)
- o Urinalysis/pregnancy test if clinically indicated

- ***Imaging***

- o Power Doppler Ultrasound (PDUS) of standard set of 26 joints and 6 tendons for grey-scale (GS), power Doppler (PD), erosions (E) and osteophytes (O) and tenosynovitis (TSV) (+/- 7 days from clinic visit)
 - To be performed prior to first administration of study treatments

- ***Adverse event recording***

- ***Initiation of DMARD treatment as per T2T*** (up to 7 days from clinic visit).

- ***Initiation of Benepali® for ARM C*** (up to 7 days from clinic visit).

- o Patients taught how to self-inject

- ***Offer IM/IA/PO corticosteroids as appropriate (in line with standard practice)***

- ***Document steroid used, dose and method of administration***

9.4 Follow up visits

9.4.1 Week 4 (Safety visit) (+/- 7 days)

As per standard clinical care/T2T, patients will undergo the following routine clinical & laboratory assessments:

- ***General***

- o Confirm eligibility and consent
- o Assess compliance with treatment
- o Clinical observations will be performed as per standard care (not required as a research parameter)
- o Medication, allergy and co-morbidity check

- ***Clinical assessment data***

- o Joint examination performed by an independent assessor:

- Tender joint count (28)
- Swollen joint count (28)
- o Disease activity score (DAS28)
- o Clinical disease activity index (CDAI)
- o Simplified disease activity index (SDAI)
- o Early morning stiffness (mins)
- o Cardio-respiratory & abdominal examinations if clinically indicated

- ***Patient reported outcomes***

- o Visual analogue scores of pain/disease activity/general health
- o Physician assessment of general health
- o HAQ-DI

- ***Laboratory Tests***

- o Routine haematology and biochemistry suitable for diagnostic investigation & therapeutic DMARD monitoring FBC, U&E, LFT & eGFR ml/min/1.73 m²
- o ESR (mm/h) & CRP (mg/L)
- o Urinalysis/pregnancy test if clinically indicated

- ***Other:***

- o Adverse event recording
- o DMARD management according to T2T and the physician's discretion. +/- IM/IA/PO corticosteroids as appropriate (in line with standard practice)
- o Document steroid used, dose and method of administration

